6.6 Limitations of the Investigation

The study is limited by the small sample size, but allows for calculations of appropriate summary statistics. There is also the possibility that patients will reach study completion of data collection prior to stent removal, due to one of the events described in Section 7.10 (e.g., death, withdrawal, reached 6 months without stent removal). [REDACTED]

7 Methods

7.1 Subject Consent

Patients who meet one of the inclusion criteria and none of the general exclusion criteria will be invited to participate in this investigation. All patients eligible for entry into the investigation will have the clinical investigation plan explained to them, as well as potential risks and benefits of their participation in the investigation. Each patient who agrees to participate will be required to sign an informed consent document prior to the procedure. A baseline evaluation to collect data should include, but is not limited to, symptoms of the condition (e.g., pain, nausea), applicable past or current medical conditions, and patient's dysphagia score. Some inclusion/exclusion criteria [REDACTED] may require evaluation immediately prior to stent placement to confirm eligibility into the study.

7.2 Medications

Pre-procedural, procedural, and post-procedural/discharge medication and therapy should be based upon clinical indication and underlying disease (i.e., standard of care). Information regarding use of acid suppression therapy and tumor reduction therapy should be captured at baseline, discharge, and throughout follow-up.

7.3 Stent Placement Procedure

Please refer to the manufacturer's IFU for stent and delivery system instructions, including general use information, patient preparation, procedural needs, wire guide use and selection, stent size selection, stent expansion/stent deployment, and delivery system removal. Dilation should be completed, as necessary, to allow complete evaluation of the lesion prior to delivery of the stent. Confirmation that the patient meets one applicable inclusion criterion, and none of the exclusion criteria [REDACTED] must be obtained prior to introduction of the stent. The IFU recommends assessment and pre-dilation of the stricture, as necessary [REDACTED]

[REDACTED] Pre-dilation can occur over several sessions per the physician's discretion prior to stent placement. There is a lasso loop with a grasping feature on both ends of

the stent to allow repositioning of the stent during the procedure, if needed (e.g., in the event of incorrect placement). [REDACTED]

At the time of the stenting procedure, the following information should be recorded, at a minimum:

- Lesion characteristics
- Stent information
- Reason/indication for stent placement
- Ability to deliver and accurately place the stent
- Device integrity
- Need for repositioning [REDACTED]

- Adverse events (including serious events) occurring during the procedure

7.4 Point of Enrollment

Point of enrollment will be based on the intent-to-treat population, and is defined to include any patient for whom the treatment procedure is initiated. More specifically, once the delivery system of the study device (Evolution® Esophageal Stent System – Fully Covered) has been inserted into the patient, this patient would be included in the intent-to-treat population. Cook intends to enroll a maximum of 130 patients to ensure that 58 patients have had endoscopic stent removal attempted after an indwell time of at least 7 days, but no more than 6 months. The first 58 patients with attempted endoscopic stent removal after an indwell time of at least 7 days, but no more than 6 months, will be included [REDACTED]. Additional analyses on remaining endpoints may be performed on all enrolled patients, as applicable, including an analysis on clinical success of the stent in benign conditions.

7.5 Post-stent Placement Procedure and Discharge

Patients should be observed for development of any complications of endoscopy procedures, esophageal dilation, or stent placement. [REDACTED]

Patients should be discharged according to institutional standards. At the time of discharge, information including, but not limited to clinical symptoms (e.g., pain, nausea) and adverse events (including serious events) occurring since the procedure should be recorded.

7.6 Follow-up Post-stent Placement

Patients will be followed after stent placement according to the schedule below unless the stent is removed (surgically or endoscopically), a non-study stent is placed, or other study exit (e.g., death, withdrawal, lost to follow-up) has occurred:

Clinic visit	7 days (range 5-12 days)
Telephone	1 month \pm 7 days
	2 months \pm 7 days
	3 months \pm 7 days
	4 months \pm 7 days
	5 months \pm 7 days
	6 months \pm 7 days

If a patient completes a required visit outside of the prescribed follow-up window, it will be recorded as a deviation from the clinical investigation plan.

Patients enrolled in the study will be followed an additional 30 days following endoscopic stent removal, unless replaced with another non-study stent. If the study stent is surgically removed (e.g., during esophagectomy), the patient will immediately exit the study. If a non-study stent is placed (either before or after stent removal), the patient will immediately exit the study (note: overlapping stents is not recommended per the IFU). If the stent removal procedure occurs at the 6-month follow-up, patients will be followed an additional 30 days following the stent removal procedure. The data collection schedule is provided in Table 2.

For all telephone contacts, a prescribed script is recommended to collect the required data. At least three attempts to contact the patient should be made and documented in the study source documents. If the patient still cannot be reached it may be considered a missed visit/telephone contact. Of note, data may be collected at a clinic visit instead of a telephone call if preferred by the patient and/or physician.

Table 2. Data collection schedule

Data collection schedule ¹	Pre-procedure	Stent placement procedure/discharge	7-day ² (5-12 days)	1-month ² (23-37 days)	2-month ² (53-67 days)	3-month ² (83-97 days)	4-month ² (113-127 days)	5-month ² (143-157 days)	6-month ² (173-187 days)	Stent removal	30 days post-stent removal
Informed Consent	X										
Inclusion/Exclusion	X	X									
Medical History	X										
Lesion Characteristics		X									
Dysphagia Score	X		X	X	X	X	X	X	X	X	X
Endoscopy ²		X								X	
Radiographic Assessment ²		X ³								X ³	
Telephone Contact ⁴				X	X	X	X	X	X		X
Clinic Visit ⁴	X	X	X							X	

¹ If a non-study stent is placed (e.g., inside the study stent or after study stent removal) or if the study stent is removed surgically, patient will exit the study immediately. If study stent is completely removed endoscopically and not replaced, patient will be followed for 30 days. If stent is not completely removed and non-study stent is not placed, patient will be followed until patient reaches 6-month follow-up or stent is completely removed.

² Additional endoscopy and/or radiographic assessment (e.g., X-ray) should be performed if clinically indicated (e.g., lack of marked improvement in dysphagia score, significant pain, suspected stent migration). Additional X-rays may be warranted in patients at higher risk for migration.

³ If stent placed for fistula, perforation, or leak, radiographic assessment (e.g., barium swallow) should be performed to confirm successful sealing of the lesion after stent implantation and to confirm lesion closure following stent removal.

⁴ Patient will be requested to provide information regarding clinical symptoms (e.g., dysphagia) and adverse event information since the last contact, if applicable, during each telephone contact and clinical visit during the patient’s study participation. Adverse events should also be reported upon awareness of the event if between telephone contacts and clinical visits.

For patients with a fistula, perforation, or leak, documentation of the original lesion closure should be obtained following stent removal (e.g., barium swallow), even if the original lesion is not identified using endoscopy at stent removal.

Additional endoscopy and/or X-rays should be performed according to standard of care if clinical symptoms persist/recur (e.g., lack of marked improvement in dysphagia score, significant pain, suspected migration). Additional X-rays may be warranted in patients at higher risk for migration (e.g., patients undergoing radiation/chemotherapy, patients with gastric surgery resulting in altered anatomy). Symptoms resulting in additional endoscopies should be recorded as adverse events.

At follow-up, the following information should be recorded, at a minimum:

- Dysphagia score
- Patient’s resumption of oral intake
- Current clinical symptoms (e.g., pain, nausea)
- Adverse events (including serious events) since last contact

7.7 Stent Repositioning

A patient may have the stent repositioned, when it is clinically indicated (e.g. sub-optimal placement after initial placement procedure, resulting in patient pain or discomfort). Please refer to the manufacturer’s IFU for information regarding stent repositioning. There is a lasso loop with a grasping feature on both ends of the stent to allow stent repositioning. [REDACTED]

[REDACTED] If the stent is repositioned, the patient will continue to be followed according to the study schedule.

If the stent is repositioned after discharge, the following information should be recorded, at a minimum:

- Reason for repositioning
- Dysphagia score (prior to stent repositioning)
- Ability to reposition stent in desired position
- Device integrity
- Adverse events (including serious events) since last contact and during procedure to reposition stent

7.8 Stent Removal

Patients will have the stent removed when it is clinically indicated based on the physician’s clinical judgment. Please refer to the manufacturer’s IFU for information regarding stent removal. The indwell time may be different depending on the indication for stent implantation.

[REDACTED]

There is a lasso loop with a grasping feature on both ends of the stent to allow stent removal. If the stent is endoscopically removed, the patient will be followed for 30 days post-stent removal unless a new, non-study stent is placed. If the stent is removed surgically (e.g., during esophagectomy), the patient will exit the study immediately.

If the stent is unable to be completely removed during the initial removal procedure, the patient will continue to be followed until the stent (or remainder of the stent) is removed, until an additional stent is implanted, or for 6 months after the initial stenting procedure, whichever comes first.

If the stent is endoscopically removed, the following information should be recorded, at a minimum:

- Reason for removal
- Dysphagia score (prior to stent removal)
- Ability to completely remove stent
- Device integrity
- Adverse events since last contact and during removal procedure (including serious events and visible tissue damage or hemorrhaging requiring immediate intervention)

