7.9 Duration of Study and Subject Participation

Patient recruitment should be completed within 24 months of initiating the study. Follow-up data will continue to be collected for six months after stent deployment for each patient in the study, unless a patient exits the study as discussed below (reminder: the patient will be followed for an additional 30 days if the stent is removed at the 6-month follow-up).

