7.10 Study Exit

A patient will be considered to have exited the study when one of the following has occurred:

- Voluntary withdrawal
- Lost to follow-up
- Death
- 30 days post endoscopic stent removal
- Stent is surgically removed (e.g., during esophagectomy)
- Non-study stent is implanted (e.g., inside study stent or after study stent is removed)
- 6 months if the stent has not been removed or replaced

After a patient exits the study, the physician may continue to follow the patient per the institution's standard of care. No additional data will be submitted to the data coordinating center once a patient has exited the study.

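### A late removal attempt that leaves stent material in place can get fewer than 30 days of event collection, and Section 7.6 conflicts with the sections that set this limit

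*Combined protocol and SAP*

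**What the plan says.** **After a complete endoscopic removal** the rule is 30 days. Section 7.8: "If the stent is endoscopically removed, the patient will be followed for 30 days post-stent removal unless a new, non-study stent is placed". Footnote 1 to Table 2 (Section 7.6): "If study stent is completely removed endoscopically and not replaced, patient will be followed for 30 days". Section 7.10 lists the same exit. Section 7.9 lets it run past month 6: "the patient will be followed for an additional 30 days if the stent is removed at the 6-month follow-up".

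**After an incomplete removal** the limit is a calendar date. Section 7.8: "If the stent is unable to be completely removed during the initial removal procedure, the patient will continue to be followed until the stent", or what is left of it, is out, another stent is implanted, "or for 6 months after the initial stenting procedure, whichever comes first". Footnote 1 says that, if no non-study stent is placed, the "patient will be followed until patient reaches 6-month follow-up or stent is completely removed". The exit list in Section 7.10 has "6 months if the stent has not been removed or replaced". None of these sets a minimum period after the attempt, and 7.10 adds that nothing more is submitted once a patient has exited.

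**At the 6-month follow-up**, the body text of Section 7.6 gives a further 30 days after a removal procedure done then. It attaches no condition on whether the stent came out.

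**Definitions (Appendix C).** An attempt also counts when removal was intended but judged not possible or not safe, so that the stent stays in. Success needs complete removal in one procedure and in one piece, with no removal-related tissue damage or bleeding seen during that procedure that needs immediate treatment.

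**The concern.** In the last month of the window, the length of safety observation after an attempt depends on how the attempt ended. A patient whose stent came out gets 30 days. A patient who still has the stent or part of it, with no surgery and no second stent, may get only a few days. Because data submission stops at exit, an event after that point is lost to the study, not merely reported late.

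Adverse-event counts after late attempts are then not like for like between complete and incomplete removals. The wording also lets two sites follow the same patient for different periods, depending on whether they apply 7.6 or 7.8.

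**Working it through.** The visible text gives no figure that depends on this follow-up length, so there is nothing of the plan's own to reproduce.

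**Inputs**
- 30 days after complete removal (7.6, 7.8, footnote 1, 7.10).
- Limit of 6 months after placement for an incomplete removal (7.8, footnote 1, 7.10).
- 6-month contact on days 173 to 187 (Table 2). I take 6 months as day 180, the centre.
- Attempt window from 7 days to 6 months (5.5.1): 180 − 7 = 173 days.

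**Step 1: days of follow-up.** For an incomplete attempt on day d, with no later removal, surgery or other stent, follow-up is 180 − d days, or 187 − d if the last contact is on day 187. The gap is 30 minus that figure, where positive.

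| Attempt on day | Incomplete, to day 180 (to day 187) | Complete | Gap |
|---|---|---|---|
| 120 | 60 (67) | 30 | none |
| 150 | 30 (37) | 30 | none |
| 160 | 20 (27) | 30 | 10 (3) |
| 170 | 10 (17) | 30 | 20 (13) |
| 175 | 5 (12) | 30 | 25 (18) |
| 180 | 0 (7) | 30 | 30 (23) |

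The gap opens after day 180 − 30 = 150, or after day 187 − 30 = 157. Footnote 1 ends at the 6-month contact, which may be as early as day 173. An attempt on day 170 would then get 173 − 170 = 3 days, so the table is not the least favourable reading.

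**Step 2: average gap.** For attempts spread evenly over days 151 to 180 (an assumption), the gap to day 180 runs 1, 2, …, 30, with mean 15.5 days. To day 187 it is zero up to day 157 and then 1 to 23, with mean 276/30 = 9.2 days.

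**Step 3: how many patients.** If attempts are spread evenly over the window (an assumption), the affected share is 30/173 = 0.173. With k incomplete attempts, P(at least one affected) = 1 − (1 − 0.173)^k:
- k = 1: 17%, expected 0.17 patients
- k = 2: 32%, expected 0.35 patients

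The share falls to (180 − 157)/173 = 13% with a day-187 contact. If 7.6 is read to cover every attempt from day 173, it is (173 − 150)/173 = 13% or (173 − 157)/173 = 9%. At 9%, two incomplete attempts give 1 − (157/173)² = 18%.

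The plan does not say how many attempts will be incomplete. As a guide, an exact one-sided binomial test of 88% on 58 patients needs at least 56 successes (tail probability 0.0239; same cut-off at 0.025 and 0.05). A positive trial would then have at most 2 failures of any kind. The test and alpha are not visible, so this is an assumption. At 88% success there would be 58 × 0.12 ≈ 7 failures. If all 7 were incomplete, the expected number affected would be 7 × 0.173 = 1.2, which is an upper figure for the cohort of 58. Attempts outside that cohort would add to it.

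**Step 4: the texts side by side.** Take an incomplete attempt made at the 6-month follow-up, on day 180.
- 7.6 (body text): follow to day 210.
- 7.8, footnote 1, 7.10: stop at day 180, or day 187 at the latest.
- 7.9: the extra 30 days apply only if the stent is removed.

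These cannot all be followed.

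**The case against.** Four points on the other side carry weight.

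- **The rule turns on incomplete removal, not on failure.** A reader might infer that every failed removal is cut short. The documents do not support that. Under Appendix C a removal also fails if the stent comes out in pieces, or with tissue damage or bleeding needing immediate treatment. If the stent is out, 7.8, footnote 1 and 7.10 give these patients 30 days. So the failures with an injury seen at the procedure and the stent out keep their full follow-up. This stands, and it limits the point.
- **There is no overall under-count.** A reader might infer that removal-related events are systematically missed after incomplete removals. Before day 150, a stent that stays in is followed for longer than 30 days. With attempts spread evenly over days 7 to 180, mean follow-up to day 180 is 173/2, about 86 days. The shortfall exists only late in the window.
- **Section 7.6 may already close the gap where it is widest.** Read literally, it gives 30 days after any removal procedure at the 6-month follow-up. But 7.9 is narrower, and 7.8, footnote 1 and 7.10 say otherwise. This therefore shows a contradiction and does not settle the matter. It also leaves attempts between about day 150 and the 6-month follow-up uncovered.
- **Little rests on it.** The primary endpoint is judged during the procedure, and events at removal are recorded then. The visible text plans no safety comparison of failed with successful removals; Section 6.5 mentions only attempted against not attempted. This stands.

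**Conclusion.** The point holds for attempts that leave all or part of the stent in place, including those that Appendix C counts although removal was judged not possible or not safe. After about day 150 (day 157 with a contact on day 187) such an attempt can get fewer than 30 days of event collection, and a complete removal on the same day gets 30. In addition, 7.6 conflicts with 7.8, 7.9, 7.10 and footnote 1 on attempts at the 6-month follow-up.

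The size is small. Probably fewer than one or two patients are involved. This rests on taking 6 months as day 180, on evenly spread attempts, and on one or two incomplete attempts. The documents give neither the timing nor the number, and Section 7.8 says that indwell time may differ by indication. Later endoscopic removal of the remainder would lower the count, as would exit for surgery or another stent. The sample of 58 and the primary test are unaffected. It is worth correcting because the cut depends on outcome, the lost data cannot be recovered, and the sections need reconciling in any case.

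**What to change.** Reconcile 7.6, 7.8, 7.9, 7.10 and Table 2 footnote 1 on data collection after an incomplete attempt. **Only for stents not completely removed**, end collection at the later of 6 months or 30 days after the latest removal attempt. Use the 30-day telephone contact that Table 2 already schedules after stent removal. State also that, when the remainder is later removed endoscopically, the usual 30 days run from that removal; 7.8 and footnote 1, read literally, stop on the day it comes out.

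Leave unchanged the 30-day exit after complete removal and the exits for surgical removal, a non-study stent, death, withdrawal and loss to follow-up. The restriction matters: applied to every attempt, the rule would hold a patient with a complete removal on day 30, who now exits on day 60, until month 6.

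With this change an incomplete attempt on day 170 is followed to day 200, and the gap is zero on every day. The latest exit is day 210 for an attempt on day 180, or day 217 for one on day 187. The cost is protocol wording, one telephone contact for probably no more than one or two patients, and a few exits up to 30 days later. It changes what is collected, not how patients are managed.

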7.9 Duration of Study and Subject Participation

Patient recruitment should be completed within 24 months of initiating the study. Follow-up data will continue to be collected for six months after stent deployment for each patient in the study, unless a patient exits the study as discussed below (reminder: the patient will be followed for an additional 30 days if the stent is removed at the 6-month follow-up).

7.10 Study Exit

A patient will be considered to have exited the study when one of the following has occurred:

- Voluntary withdrawal
- Lost to follow-up
- Death
- 30 days post endoscopic stent removal
- Stent is surgically removed (e.g., during esophagectomy)
- Non-study stent is implanted (e.g., inside study stent or after study stent is removed)
- 6 months if the stent has not been removed or replaced

After a patient exits the study, the physician may continue to follow the patient per the institution's standard of care. No additional data will be submitted to the data coordinating center once a patient has exited the study.

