4.1 Risks and Foreseeable Adverse Events

As part of the stent implantation and removal, endoscopic procedures may also need to be performed. These procedures are generally recognized as safe, although risks have been noted with these procedures. Potential risks associated with endoscopic procedures and/or esophageal stenting and removal include, but are not limited to:

- Perforation
- Hemorrhage
- Aspiration, reflux, vomiting
- Fever, infection
- Allergic reaction (e.g., to medication)
- Hypotension
- Respiratory compromise, depression, or arrest
- Cardiac arrhythmia or arrest
- Stent misplacement and/or migration
- Tumor and tissue ingrowth and overgrowth, 
-  
- Dysphagia 
- Esophageal ulceration and erosion
- Tear/tissue damage 
- Wire entrapment
- Nausea
- Pain
- Foreign body sensation or reaction
- Esophagitis

- Edema
- Food bolus impaction
- Gas bloat syndrome
- Sensitivity to device components
- Fistula (e.g., involving trachea, bronchi, or pleural space)
- Intestinal obstruction secondary to migration
- Mediastinitis or peritonitis
- Airway compression
- Tracheal obstruction
- Compression of adjacent structures
- Death (other than due to normal disease progression)

It is also important to note that the decision to remove or reposition the stent is based on the physician's clinical judgment. Pre-existing conditions (e.g., stricture, fistula, perforation, leak) may not be healed at the time of stent removal and may require additional intervention.

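### Section 7.10 stops data at exit and surgical stent removal is an immediate exit, so the later outcome of a complication managed by explant can be lost; 7.10 and 11.2 need reconciling.

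*Combined protocol and SAP*

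**What the plan says.** Section 7.10 lists the events that end participation. Surgical removal of the stent is one of them. The section then closes the data flow: "No additional data will be submitted to the data coordinating center once a patient has exited the study". It adds that the physician is free to go on following the patient under local standard of care.

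The timing of exit at surgical removal is stated three more times:

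- Section 7.6, text: "If the study stent is surgically removed (e.g., during esophagectomy), the patient will immediately exit the study".
- Section 7.8: "If the stent is removed surgically (e.g., during esophagectomy), the patient will exit the study immediately".
- Table 2, footnote 1: "if the study stent is removed surgically, patient will exit the study immediately".

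Endoscopic removal is treated differently. Section 7.6 says: "Patients enrolled in the study will be followed an additional 30 days following endoscopic stent removal, unless replaced with another non-study stent". Section 7.8 also sets a minimum data list, covering the reason for removal and adverse events during the procedure, but introduces it with "If the stent is endoscopically removed, the following information should be recorded, at a minimum". No matching list for surgical removal is visible.

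On safety reporting, section 11.2 asks that forms for adverse device effects and serious adverse events reach the data coordinating center promptly once the site learns of the event. Section 11.1 describes review of patient data at that center as part of getting events correctly to the DSMB. Section 4.1 names "Mediastinitis or peritonitis" among the foreseeable risks, along with perforation, fistula, intestinal obstruction after migration, and death.

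**The concern.** A complication of the stent may itself be the reason for an operation that takes the stent out. In such a patient the harm triggers the exit, and the exit closes data submission. What happened next, whether recovery, continuing illness or death, would be missing because of the harm and not by chance. A patient whose stent comes out endoscopically without incident normally has 30 further days of follow-up.

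At stake is the completeness of the safety summary and of what the DSMB sees for what may be the most serious device events. In a single-arm study of at most 130 patients, such outcomes carry weight one by one. The exit rule also does not separate a planned esophagectomy from an explant for a complication, and the removal data list in 7.8 does not visibly cover surgical removal. The visible text therefore does not ensure that the two can be told apart afterwards.

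**Working it through.** No figure in the plan bears on this point, so the check consists of following one patient through the rules. The case assumed is a device complication with the stent in place, managed by an operation that removes the stent. That such operations occur is a clinical assumption; section 4.1 lists the harms but does not say how they are treated.

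1. **Onset.** The patient is still in the study. Section 11.2 and Table 2 footnote 4 (report on awareness between contacts) both apply, so the event is reportable.
2. **Operation.** Sections 7.6, 7.8, 7.10 and Table 2 footnote 1 agree that the patient exits at once. Planned follow-up after surgical removal is 0 days, against 30 days after endoscopic removal with no new non-study stent.
3. **Record of the removal.** The minimum data list in 7.8 applies to endoscopic removal. Nothing visible requires the reason for a surgical removal.
4. **Outcome after the operation.** Section 7.10 bars further submission to the data coordinating center. Section 11.2 has no end date, but it has no rule for following an open event to its outcome and does not say that it overrides 7.10.
5. **Can the site resolve this itself?** Section 8 allows departures from the plan only with prior sponsor authorization or in an emergency that touches subjects' rights, safety or well-being. A site that follows 7.10 literally would stop reporting.
6. **Who sees the outcome.** The route to the DSMB in 11.1 and the main route to the sponsor in 11.2 run through the data coordinating center, so the bar falls on both. IRB notification under 11.2 is separate but does not feed the trial database.
7. **Hypotheses.** The primary endpoint (6.1.1, Appendix C) is judged at the endoscopic retrieval procedure. Clinical success in benign indications (6.1.2, Appendix C) is judged at the 7-day follow-up. The later outcome of a complication enters neither.

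Two boundaries follow. The gap arises when surgery removes the stent; an operation that leaves it in place does not by itself end participation. The same bar meets a serious event still open at any other exit, such as placement of a non-study stent (also an immediate exit), the 30-day post-removal contact or the 6-month contact. There the exit need not be caused by the harm.

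The sections on exit, follow-up, withdrawal, adverse event reporting, safety monitoring, early termination and definitions show no exception to 7.10. No redaction is marked in 7.10, 11.1 or 11.2. Section 7.8 has redacted text, so the accurate statement is that no exception is visible.

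**The case against.** The strongest reply is that 7.10 is not meant literally. Death and voluntary withdrawal are themselves exits, yet 7.11 requires termination data for withdrawn patients and 10.1 provides for data queries. On a workable reading, scheduled follow-up stops and records of known events are still completed. Section 11.2 has no end date. Other routes to the sponsor exist as well: under 10.1 investigators supply clinical data to the sponsor, and under Appendix B, part C, the monitor reports potentially reportable events. The 7.10 bar names only the data coordinating center.

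Much of this stands. A reader might infer that stent complications needing surgery go unreported, or that the sponsor is wholly cut off. The documents do not support either inference, because onset is reportable and those other routes remain. None of these provisions, however, creates a duty to obtain the outcome after exit, and none is written as an exception to 7.10.

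It is also fair to say that the only example the plan gives of surgical removal is esophagectomy. Section 5.3 excludes patients with malignant indications who are not candidates for tumor reduction therapy or resection, so planned surgery is a foreseeable route. How often explant would follow a device complication is not stated.

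Finally, every study has a data cut-off. That reply has force for events open at the 30-day or 6-month contact. It has less force where the event itself brought the cut-off forward.

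**Conclusion.** The point holds as an unreconciled tension between 7.10 and 11.2. It matters most when a device- or procedure-related serious event leads to surgical removal of the stent. Read as written, 7.10 keeps the later course of that event, including a related death, out of the trial database and off the described route to the DSMB. Safety summaries may then understate the outcomes of such events.

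The size cannot be given. The documents state no rate of surgical explant for complications and no probability of death after it. An assumed explant rate applied to 130 patients would give the chance of seeing an explant, not of missing a death, and 130 is an enrollment maximum. A reader might also infer that device-related mortality is biased downward. The text shows only that such deaths could be missed, not that any would be. No visible endpoint is device-related mortality, although the secondary endpoints are partly redacted.

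Neither hypothesis is affected. The conclusion rests on two assumptions: that some complications are managed by explant, and that no redacted text holds an exception. It is an inexpensive improvement to make, not a flaw that undermines the study's main result.

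**What to change.** Reconcile 7.10 with 11.2 by adding one reporting exception to 7.10, cross-referred from 7.6, 7.8 and Table 2 footnote 1:

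- It covers a device- or procedure-related serious adverse event that is open at exit, in particular one that led to surgical removal of the stent.
- The site submits the outcome of that event (resolved, ongoing or death) on the existing adverse event form, from available care records, for a stated period such as 30 days after exit.
- It is subject to consent and does not apply where consent to data use has been withdrawn.
- Deaths reported this way enter the safety summary and the DSMB review.

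A planned esophagectomy without such an event exits as now. The change concerns data reporting only and alters no clinical management.

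The cost is a protocol wording change with sign-off (15.1) and IRB handling, a few late form entries, and a short delay in closing those records. Continued care by the study physician is optional under 7.10, so records may be incomplete for some patients. The consent pages are not among the documents reviewed, so whether consent already covers data after exit must be checked. The safety table may look slightly worse.
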